7.5.3 Smoking Assessment (Part C only)

The following data will be assessed for the Safety population of Part C and will be listed and summarized using descriptive statistics:

- Expired carbon monoxide (ECO) level
- Plasma cotinine level
- Number of cigarettes smoked (smoking log)
- Minnesota Nicotine Withdrawal Scale (MNWS) responses
- Questionnaire on Smoking Urges – Brief version (QSU-Brief) responses
-

Actual values and change from baseline will be presented in a listing and will be summarized by Symptoms (if applicable) and visit.

8 SAFETY ANALYSIS

Unless otherwise specified, all available data will be listed and summary tables for safety assessments will be presented for the safety population as detailed in Table 8.

Table 8: Data presentations for safety assessments

Data	Variables	Presentation
Adverse events	Adverse event (AE) description, onset and resolution date and time, time from product use, severity, relationship to study drug, action taken, and outcome	
Listing (by subject, Cohort and treatment): L16.2.7.1
 
Summary tables, including number and percentage of subjects experiencing:
 
 • Reported AEs, • Treatment-emergent adverse events (TEAEs), • Drug-related TEAEs (i.e. those with a relationship classified as Definite, Probable, Possible and Unlikely), • TEAEs by relationship to study treatment (i.e., Definite, Probable, Possible, Unlikely and Not related), • TEAEs by severity, • Serious TEAEs, • Study drug-related serious TEAEs, • TEAEs leading to withdrawal, and • TEAEs with an outcome of death. 
Note: includes coded terms (system organ class [SOC] and preferred term [PT]) T14.3.1.1.1 – T14.3.1.4.4, T14.3.2.1 and T14.3.2.2

Concomitant medications	All medications taken during the study (as defined in the protocol and including prior medications that are continued), dose, units, frequency, formulation, route, indication/ reason taken, and date and time	
Listing
 
Note: includes coded terms (anatomic therapeutic chemical [ATC] level 1 and preferred name)
 
L16.2.7.2

Extent of exposure	Category of drug, treatment, total dose, dose unit, formulation, frequency, administration date and time, route of administration, Was the treatment administered as specified in the protocol? and dosing comments	
Listings:
 
L16.2.5.1
 
L16.2.5.2
 
L16.2.5.3

Clinical laboratory	Laboratory results (refer to section)	Listings:

Data	Variables	Presentation
evaluations	9.2 for parameters)	
 • All laboratory values by visit L16.2.8.1.1 – L16.2.8.1.7 • All out-of-range laboratory values • All clinically significant laboratory values T14.3.4.1.1 – T14.3.4.1.2 
Summary tables
 
 • Summary of continuous tests • Summary of categorical tests 
T14.3.4.2.1 – T14.3.4.5.4

Vital signs	Blood pressure, pulse, respiratory rate and body temperature	
Listings:
 
 • All vital signs values L16.2.8.3.1 – 16.2.8.3.2 • All out-of-range vital signs values • All clinically significant vital signs values T14.3.5.1.1 – T14.3.5.2.4 
Summary tables:
 
 • Summary of vital signs by visit T14.3.5.3.1 – T14.3.5.4.4
Physical examination	Physical examination findings	
Listings:
 
 • All Physical examination findings • L16.2.8.2 All clinically significant Physical Examination findings T14.3.6.1
Electrocardiograms (ECGs)	ECG interpretations and findings	
Listings:
 
 • all 12-Lead ECGs findings L16.2.8.4 
Summary tables:
 
 • summary of ECG assessments by visit • all out-of-range ECG values • all clinically significant ECG values T14.3.7.1.1 – T14.3.7.1.2 • all out-of-range ECG values T14.3.7.2.1 – T14.3.7.2.4
C-SSRS	Columbia Suicide Severity Rating Scale	
Listing:
 
L16.2.9.1

Note: Sub-bullets denote individual listings or tables to be generated.

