## 3.5.2. Cohort Stopping Rules

If any of the following safety concerns are observed, dosing of all subjects at the given dose level or higher will be suspended/halted and all available data will be evaluated by the DSMB.

Dose continuation (remaining subjects within a cohort or remaining dosing for a subject) or escalation should not proceed for any of, but not limited to, the following reasons:

- If one SBP-9330-related SAE occurs in a cohort
- Severe AE at least possibly related to SBP-9330 in two or more subjects in the same cohort\*
- Other findings that, at the discretion of the DSMB or Sponsor, indicate further dosing should be stopped

\* Prior to suspending the cohort, if severe AEs are reported in two or more subjects at a given dose level, consideration should be given to the treatment assignment (SBP-9330 or placebo). After causality assessment, the Investigator (or designee) should open the individual randomization code to verify the treatment received. Dosing at the given dose level may continue if only one subject received SBP-9330 and the other(s) received the placebo.

Subjects experiencing severe AEs will be followed up with serial measurements of the related clinical parameter(s), as per medical judgment, until resolution, stabilization, or until the subject is lost to follow-up.

Dose escalation will be discussed during the DSMB meeting and may be stopped depending on Principal Investigator's or Sponsor's decision, based on but not limited to the following:

- New clinically significant abnormalities in physical examination, 12-lead ECG, or vital signs in two or more subjects
- Overall pattern of clinical changes or symptoms that may have appeared minor in terms of an individual AE or subject, but which collectively present a safety concern
- Clinically significant changes in organ-specific laboratory parameters (e.g., liver function enzymes in one or more subjects)
- Pattern of laboratory changes (e.g., a consistent increase or decrease in two or more subjects or within or across dosing cohorts) that might indicate an overall safety concern

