#### 7. ADVERSE EVENTS DOCUMENTATION

#### 7.1. **Definitions**

An AE is defined as any untoward medical occurrence in a subject administered an investigational product and which does not necessarily have a causal relationship with the treatment. An AE can therefore be any unfavorable and unintended sign (including for example, a clinically significant abnormal clinical laboratory finding), symptom, or disease temporally associated with the use of an investigational product, whether or not related to the investigational product.

A suspected adverse reaction (SAR) is any AE for which there is a reasonable possibility the drug caused the AE. 'Reasonable possibility' means there is evidence to suggest a causal relationship between the drug and the AE. A suspected adverse reaction implies a lower degree of certainty about causality than adverse reaction, which means any AE caused by a drug.

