## 7.3. Causality Assessment

An Investigator will determine the relationship of any AE to the study drug using the guidelines presented in Table 14.

Table 14 Adverse Event Relationship to Study Drug

Relationship to Drug	Comment
Definite	A clinical event, including laboratory test abnormality, occurring in a plausible time relationship to drug administration and which cannot be explained by concurrent disease or other drugs or chemicals. The response to withdrawal of the drug (de-challenge) should be clinically plausible. The event must be definitive pharmacologically or phenomenologically using a satisfactory rechallenge (the drug is readministered to determine if the same reaction occurs) procedure if necessary.
Probable	A clinical event, including laboratory test abnormality, occurring in a plausible time relationship to drug administration and which cannot be explained by concurrent disease or other drugs or chemicals. The response to withdrawal of the drug (de-challenge) should be clinically plausible.
Possible	A clinical event, including laboratory test abnormality, with a reasonable time sequence to the drug administration, but which could also be explained by concurrent disease or other drugs or chemicals. Information on drug withdrawal may be lacking or unclear.
Unlikely	A clinical event, including laboratory test abnormality, with a temporal relationship to drug administration which makes a causal relationship improbable and in which other drugs, chemicals or underlying disease provide plausible explanations.
Not related	Any event that does not meet the above criteria; there is sufficient information that etiology of the event is in no relation to the study drug.

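### SAP Table 8 counts adverse events graded Unlikely as drug-related, which does not fit the protocol's own causality scale

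*SAP*

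**What the plan says.** SAP Section 8, Table 8, lists the AE summaries as numbers and percentages of subjects. One is "Drug-related TEAEs (i.e. those with a relationship classified as Definite, Probable, Possible and Unlikely". The next is "TEAEs by relationship to study treatment (i.e., Definite, Probable, Possible, Unlikely and Not related", so all five grades are also tabulated. A later row, "Study drug-related serious TEAEs", has no definition of its own. SAP Section 8.1 then names two sets of frequency tables by system organ class and preferred term, one for all TEAEs and one for study drug-related TEAEs. Both are shown by cohort with pooled placebo.

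The grades come from Protocol Section 7.3, Table 14. The entry for Unlikely reads: "temporal relationship to drug administration which makes a causal relationship improbable and in which other drugs, chemicals or underlying disease provide plausible explanations". By contrast, the lowest grade, Not related, applies where "there is sufficient information that etiology of the event is in no relation to the study drug".

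Two other protocol passages give relatedness a meaning. Section 7.1 ties a suspected adverse reaction to a reasonable possibility, which it explains as meaning that "there is evidence to suggest a causal relationship between the drug and the AE". Section 3.5.2 lists as a cohort stopping criterion: "Severe AE at least possibly related to SBP-9330 in two or more subjects in the same cohort".

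**The concern.** A table titled drug-related is read as showing events that the investigator thought the drug may plausibly have caused. Under the SAP's definition it also holds events that the investigator judged improbable and could explain otherwise. The SAP gives no reason for this choice.

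At stake is the meaning of one of the two AE table sets broken down by system organ class and preferred term. Active cohorts have 6 or 8 subjects, so one or two subjects can make or hide an apparent dose pattern in the drug-related rows. The definition applies to placebo as well, where pooled groups are also small.

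**Working it through.** The documents state no figure that depends on this definition, so there is nothing to reproduce. The check is a comparison of wording, followed by the size of the effect per subject.

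**Step 1: where each passage puts Unlikely**

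| Source | What it says about relatedness | Unlikely counted? |
|---|---|---|
| SAP Table 8, drug-related TEAEs | Four of five grades, named | Yes |
| Protocol 7.3, Table 14 | Causation improbable, other explanations plausible | Meaning points to no |
| Protocol 7.1, suspected adverse reaction | Needs evidence suggesting causation | Meaning points to no |
| Protocol 3.5.2, severe-AE rule | Possible or above | No |
| Protocol 3.5.1, 3.5.2 (SAE rule), 3.5.3 | Says related, gives no grade cut-off | Not stated |

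Wherever the protocol gives relatedness a meaning, Unlikely falls on the other side from where the SAP puts it. The protocol never groups the five grades into related and not related for reporting.

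**Step 2: which subjects change**

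Table 8 counts subjects. A subject enters the overall drug-related row only because of the broad definition if at least one TEAE is Unlikely and none is Possible or higher. Within a system organ class or preferred term row, the same condition applies to the subject's events in that row.

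**Step 3: size per subject**

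One such subject adds 100/n percentage points. The n come from the planned allocation: 6 active and 2 placebo per Part A cohort, 8 active and 2 placebo per Part B or C cohort.

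| Group | n | Points per subject |
|---|---|---|
| Part A active cohort | 6 | 100/6 = 16.7 |
| Part B or C active cohort | 8 | 100/8 = 12.5 |
| Part A pooled placebo, five cohorts | 10 | 100/10 = 10.0 |
| Part A pooled placebo, without A3 | 8 | 100/8 = 12.5 |
| Part B pooled placebo, 3 to 4 cohorts | 6 to 8 | 16.7 to 12.5 |
| Part C pooled placebo, 2 to 3 cohorts | 4 to 6 | 25.0 to 16.7 |

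Part A pooled placebo is shown both ways because SAP Section 8.1 leaves A3 out of the SAD columns, while Section 9.1 includes A3 fasted.

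**Step 4: how likely a change is**

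The documents give no rate of Unlikely events. Assume a probability p that a subject meets the Step 2 condition for the overall row, independently between subjects. The chance of at least one such subject in a cohort is 1 − (1 − p)^n.

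| p (assumed) | n = 6 | n = 8 |
|---|---|---|
| 5% | 0.27 | 0.34 |
| 10% | 0.47 | 0.57 |
| 20% | 0.74 | 0.83 |
| 30% | 0.88 | 0.94 |

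For example, with p = 10% and n = 6: 1 − 0.9^6 = 1 − 0.531 = 0.47.

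**The case against.** The strongest reply is that nothing is hidden. The definition is explicit, applies to both arms and errs toward over-attribution. The five-grade table sits beside it, and the listing carries the relationship for every event. The protocol asks only for descriptive AE summaries and sets no related/not-related split, so the SAP breaks no stated rule.

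Much of this stands, and it rules out several stronger readings:

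- A reader might infer that the primary safety result is wrong. It is not: Protocol Section 8.3.1 defines the endpoint by incidence and severity of AEs, without regard to causality. The all-TEAE, severity and serious-TEAE summaries do not change.
- A reader might infer that stopping decisions are affected. The stopping rules do not refer to the SAP tables. The Possible cut-off belongs to the severe-AE rule only, so it cannot be used to say how an Unlikely serious event would be treated under the SAE rules.
- A reader might infer that SAP Section 11, which declares no changes, is false. With no protocol-specified grouping to depart from, that is not shown.
- A reader might take the drug-related serious row to be misdefined as written. It has no definition; carrying the parenthesis over to it is a natural inference, but still an inference.
- A reader might estimate a several-fold overstatement from event counts. Table 8 counts subjects, so such a ratio does not describe it.

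Two parts of the reply do not hold. First, the five-grade table may not allow the narrower count to be recovered. The SAP does not say whether a subject with several TEAEs is counted once, at the highest grade, or under each grade; if under each, adding three rows double-counts. The listing would permit a hand recount. Second, the fully inclusive view is already given by the all-TEAE table. A drug-related table adds information only if it separates plausible from improbable causation.

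**Conclusion.** The inconsistency is real and modest. The SAP's drug-related category includes a grade that the protocol describes as improbable causation, and no reason is given. The effect is confined to the drug-related rows and, if the same definition is carried over, the drug-related serious row.

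The per-subject sizes in Step 3 assume full enrolment as planned. The chances in Step 4 rest on assumed rates and show only that a change in cohorts this small is plausible. No claim is made about the direction of any active-versus-placebo difference, because the definition acts on both arms. I rate this a minor to moderate consistency correction, not a condition for the analysis to go ahead.

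**What to change.** In SAP Table 8, define drug-related TEAEs as Definite, Probable or Possible, and state that the same definition governs the study drug-related serious TEAE row. Keep Unlikely visible in the existing by-relationship table. The protocol does not dictate this cut for reporting, but it is the one that best fits Table 14, Section 7.1 and the only threshold the protocol states. If the sponsor prefers the broad grouping, the alternative is to give the reason, footnote the affected tables and record the choice in SAP Section 11.

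The cost is one phrase and one derivation flag, with no new data. Reported drug-related counts may be smaller. The change should be made before database lock, because SAP Section 9 labels analyses outside the plan that are done after lock or unblinding as post hoc and exploratory. No change to the stopping rules is proposed.

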8.1 Adverse Events

An AE is defined as any untoward medical occurrence in a clinical investigation subject administered an investigational product and which does not necessarily have a causal relationship with the treatment. An AE can therefore be any unfavorable and unintended sign (including a clinically significant abnormal laboratory finding, for example), symptom, or

disease temporally associated with the use of an investigational product, whether or not related to the investigational product.

Treatment emergent adverse events (TEAEs) are AEs not present prior to the exposure to study treatment or AEs already present that worsen in intensity or frequency following exposure to study treatment. All AEs reported following exposure to study treatment are considered TEAEs.

All TEAEs will be assigned to a treatment using the following rules:

- A TEAEs will be assigned to the last treatment taken by the subject where the date and time of the last treatment dosing is on or before of the start date and time of the event. Such assignment will be performed irrespective of any washout period between the start and stop dates of the TEAE.
- Any TEAE started during the follow-up period will be assigned to the last treatment that the subject has taken.
- In case that the time of onset or time of resolution is unknown, worst case scenario will be considered. For the onset, 00h01 will be the time considered. For the resolution time, if the time is unknown, 23h59 will be the time considered.

Frequency tables summarizing all TEAEs and all study drug-related TEAEs (including SOC and PT) will be presented by Part A- SAD (Cohorts A1, A2, A4, A5, Pooled Placebo and Overall), Part A food-effect cohort (SBP-9330, Placebo and Overall), Part B – MAD (Cohorts B1, B2, B3, B4, Pooled Placebo and Overall) and Part C – Smoker (Cohorts C1, C2, C3, Pooled Placebo and Overall) as described in Table 8.

All adverse events will be presented in a listing as well, by study part, cohort, subject and treatment.

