## 7.4. Adverse Event Monitoring

For the purposes of this study, the monitoring period for AEs extends from the pretrial evaluation until the Follow-up Visit. From Screening to the first dose of the study, AEs will be recorded as screening events or as part of the medical history, as applicable. AEs occurring after initiation of study drug will be indicated as TEAEs in the clinical study report.

Altasciences Project Number: CNO-P5-319

Subjects will be questioned on their health status at the beginning of each study period and before each departure from the CRU. Open-ended questions will be asked.

During the study, all AEs spontaneously reported by the subject, observed by the clinical staff or elicited by general questioning will be recorded for all subjects and reported in the CRF.

If necessary, every effort will be made to obtain an adequate follow-up of the subjects. Should any subject choose to withdraw from the study, they will be advised of the safety precautions to be taken.

Any AE which remains unresolved as of the last visit will require an evaluation and follow-up until the AE has been resolved or a reasonable explanation for its persistence found, or is deemed mild and safely resolving.

In the case of AEs deemed related to the Investigational Product, every effort will be made to determine the final outcome.

It is an investigator's responsibility to ensure that subjects experiencing AEs receive appropriate follow-up treatment where required, and that every action is well documented.

Classification of AEs will be performed by System Organ Class (SOC) and Preferred Term (PT) using the Medical Dictionary for Regulatory Activities (MedDRA), version 23.0 or higher.

Concomitant medications will be coded using the World Health Organization drug dictionary (WHO-DDE March 2019 or later).

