9.1 Safety Analysis Presentation

Adverse events and medical history will be classified using the Medical Dictionary for Regulatory Activities (MedDRA) terminology version 24.0 as defined in the study data management plan (DMP).

Prior and concomitant medications will be coded with the World Health Organization Drug Dictionary- Enhanced (WHO-DDE) March 2021 as defined in the study DMP.

In general, all safety summary tables will be presented for the safety population. Summaries will be presented for each study part as below:

- Part A- SAD (Cohorts A1, A2, A3 fasted, A4, A5, Pooled Placebo and Overall)
- Part A food-effect cohort (SBP-9330, Placebo and Overall)
- Part B – MAD (Cohorts B1, B2, B3, B4, Pooled Placebo and Overall)
- Part C - Smoker (Cohorts C1, C2, C3, Pooled Placebo and Overall)

In general, the data listings will include all enrolled subjects up to the point of study completion or discontinuation; exceptions will be listings pertaining to a subset of subjects only (e.g., subjects with protocol deviations) or a subset of records/events (e.g., abnormal laboratory values).

Categorical variables will be summarized using the PROC FREQ procedure. Continuous variables will be summarized using the PROC UNIVARIATE procedure. For natural log (ln)-transformed endpoints, geometric mean, geometric standard deviation (SD), and coefficient of variation (CV%) will also be presented.

The following general comments also apply to all statistical analyses and data presentations:

- Duration variables will be calculated using the general formula: (end date - start date) +1.
- If the reported value of a clinical laboratory parameter cannot be used in a statistical summary table (e.g., a character string is reported for a parameter of the numerical type), a coded value must be appropriately determined and used in the statistical analyses. In general, a value or lower and upper limit of normal range such as ' <10 ' or ' ≤ 5 ' will be treated as '10' or '5' respectively, and a value such as ' >100 ' will be treated as '100'. However, the actual values as reported in the database will be presented in data listings.

- When assessments are repeated for a given time point or performed at unscheduled times, only the result which is the closest to the dosing time will be included in summary tables.

In general, summary statistics for raw variables (i.e., variables measured at the study site or central laboratory) will be displayed as follows:

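### An unknown AE onset time set to 00h01 falls before the morning dose: on the first dosing day no dose qualifies, and in Cohort A3 a fed-day event is linked to the fasted dose

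*SAP*

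**What the plan says.** SAP 8.1 links each TEAE to a treatment by the clock. The event goes to the last treatment the subject took, "where the date and time of the last treatment dosing is on or before of the start date and time of the event". A gap between periods does not break the link: "Such assignment will be performed irrespective of any washout period between the start and stop dates of the TEAE". A second rule covers follow-up only. A third treats unknown clock times as a worst case: "For the onset, 00h01 will be the time considered", with 23h59 for resolution. Nothing in the section stops the imputed onset from falling before that day's dose.

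Protocol 5.3 places dosing in the morning. In Cohort A3 (SAP 3.1.1) each subject takes the same product twice, fasted in Period 1 and fed in Period 2, with 7 to 14 days between.

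Other statements decide how far the rule reaches:

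- TEAE status, SAP 8.1: "All AEs reported following exposure to study treatment are considered TEAEs". Protocol 7.4 keeps pre-dose events apart: "From Screening to the first dose of the study, AEs will be recorded as screening events or as part of the medical history".
- TEAE table columns, SAP 8.1: "presented by Part A- SAD (Cohorts A1, A2, A4, A5, Pooled Placebo and Overall), Part A food-effect cohort (SBP-9330, Placebo and Overall").
- Safety summary columns in general, SAP 9.1: "Part A- SAD (Cohorts A1, A2, A3 fasted, A4, A5, Pooled Placebo and Overall").
- AE listing, SAP 8.1: "All adverse events will be presented in a listing as well, by study part, cohort, subject and treatment".

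**The concern.** The rule exists to tie an event to the exposure that preceded it. An early imputed onset is the worst case for duration. It is not the worst case for attribution, because on a dosing day it places the event before the dose that may have caused it.

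A3 is the only cohort with a washout and the only one in which a subject has two dosing conditions to tell apart. The washout clause and the A3 fasted column therefore have an effect only there, and there the rule picks the wrong condition on the fed dosing day. On the first dosing day, a 00h01 onset also clashes with the part of the TEAE definition that requires the event to be absent before exposure. AE incidence is a primary endpoint, so the handling of such events should be written down and not left to the program.

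**Working it through.** The plan gives no figure to reproduce here, so the check applies the SAP 8.1 rule literally.

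Inputs:

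- Imputed onset 00h01 on the onset date (SAP 8.1).
- Assigned dose = the latest dose with dose time ≤ onset time (SAP 8.1).
- Dose time: morning (Protocol 5.3). The hour is not given; I assume a range of 06:00 to 11:59 and checked 06:00, 08:00, 10:00 and about 11:59.
- A3 washout 7 to 14 days (SAP 3.1.1); both ends checked.
- Parts B and C: once daily for 14 days (SAP 3.1.2 and 3.1.3).
- Planned active:placebo numbers: 6:2 per Part A cohort, 8:2 per Part B or C cohort.

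| Onset day, time unknown | Dose selected as written | Dose selected if onset is not earlier than the dose |
|---|---|---|
| Day 1, Parts A (Period 1), B and C | none: 00h01 precedes the first dose | Day 1 dose |
| A3 Period 2 Day 1, washout 7 or 14 days | fasted Period 1 dose | fed Period 2 dose |
| Days 2 to 14, Parts B and C | previous day's dose, same treatment | that day's dose, same treatment |

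The result is the same at every dose time and both washouts. An A3 event with a recorded onset one hour after the fed dose is linked to the fed dose, so the error comes only from the imputed time.

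Effect on the outputs:

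- **SAP 8.1 text and columns.** The event stays a TEAE, A3 is not in the SAD table, and the food-effect table is not split by meal. Change: 0 points in every TEAE table.
- **SAP 9.1 columns.** One active fed-day event placed in A3 fasted adds up to 1/6 = 16.7 points. It adds nothing if the subject is already counted there. The error can arise on 6 + 2 = 8 planned Period 2 dosing days.
- **TEAE status derived from the imputed time.** One subject's only event would be lost: 1/6 = 16.7 points in a Part A active column, or 1/8 = 12.5 points in Part B or C.

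The column lists differ whether or not any time is missing. Planned Part A SAD numbers are:

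- SAP 8.1 (A1, A2, A4, A5): 4 × 6 = 24 active and 4 × 2 = 8 placebo, total 32.
- SAP 9.1 (A3 fasted added, assuming A3 placebo is pooled): 5 × 6 = 30 active and 5 × 2 = 10 placebo, total 40.

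One pooled-placebo subject is 1/8 = 12.5 points under the first list and 1/10 = 10.0 points under the second.

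**The case against.** The strongest reply is that SAP 8.1 assigns events to a treatment, and the documents use that word for the arm (SAP 3.1.1 and 3.5). Each subject has one cohort and one arm, and an A3 subject takes the same product in both periods. An event with no qualifying dose time still has an unambiguous treatment. This stands as far as the arm goes. It does not remove the point: if fasted and fed were never separated, neither the washout clause nor the A3 fasted column would have anything to act on.

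A reader might infer three stronger things that the documents do not support:

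- **First-day events drop out of the TEAE counts.** SAP 8.1 classes events reported after exposure as TEAEs without using the imputed time, and Protocol 7.4 records pre-dose events separately.
- **The AE listing will show the wrong meal condition.** Meal is not a stated key of that listing, stratification by meal is specified for the PK outputs (SAP 7.5), and layouts are in a separate document (SAP 12). SAP 9.4 says presentations show data as recorded, so a missing time may simply appear as missing. The listing is affected only if it shows period or meal condition.
- **The time from product use in SAP Table 8 will be wrong.** That follows only if it is computed from the imputed time, which the SAP does not say.

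The trigger is also probably rare, since every dosing day falls within confinement. Still, Protocol 7.4 has AEs elicited by open questioning as well, so some onset times may rest on recall.

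On the column lists, SAP 9.1 speaks in general terms and SAP 8.1 specifically about TEAE tables, so 8.1 may reasonably be read as governing. The SAP does not say so, and the matter is separate from the onset rule.

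**Conclusion.** The point holds as a minor defect in a written rule. For unknown onset times on a dosing day, the rule finds no dose on the first dosing day and the wrong A3 condition on the fed day. This needs only that dosing is later than 00h01, which morning dosing ensures.

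Under SAP 8.1 as written, the effect on TEAE tables is zero and no event moves between SBP-9330 and placebo. The 16.7-point shift in A3 fasted depends on using the SAP 9.1 columns. The first-day shifts of 16.7 or 12.5 points depend on a program deriving TEAE status from the imputed time, against the SAP 8.1 text. How often times will be unknown cannot be judged from the documents. Confidence is high in the clock logic; the consequences are conditional.

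**What to change.** In SAP 8.1, replace the onset rule with:

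*If the onset date is a dosing date and the onset time is unknown, onset is set to the time of the first dose on that date, unless the record shows it began before dosing; on other dates 00h01 is used.*

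Leave TEAE status to the existing SAP 8.1 sentence. Tying it to an imputed time is unnecessary.

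As a separate correction, give one AE column list in SAP 8.1 and 9.1. It should say whether A3 fasted belongs in the Part A SAD table, whether A3 placebo is pooled there, and whether the food-effect table is split by meal.

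The cost is a few SAP sentences and minor programming. The downside is that a few truly pre-dose events with a missing time may be linked to that day's dose, and derived durations become some hours shorter.
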